E. Statistical Considerations. This study aims to develop and pilot a novel psychosocial symptom management intervention for AYA's with advanced or recurrent cancer and is not designed to make conclusions about efficacy without further study.⁹⁶ Sample size estimates are based on pragmatics of recruitment over the study timeframe as well as our ability to obtain sufficient data to understand the experiences of the target population and examine intervention feasibility and acceptability. Information gathered will inform the design of future trials. Based on our past published work^{9,76} using focus groups to develop symptom management interventions, a sample size of N=28 (n=16 AYAs, n=12 caregivers) is sufficient to obtain information to confirm, and, when necessary, adapt proposed intervention content to meet the needs of AYAs with advanced or recurrent cancer. N=40 AYAs will participate in the pilot RCT. The sample size accounts for 20% attrition, which was derived from our prior work (10-15%)^{7,9,10} and attrition rates for AYAs with cancer receiving mHealth interventions (12-21%).⁹⁷⁻⁹⁹ The RCT sample size (intervention: n=24, control: n=16) was derived from published recommendations¹⁰⁰ and our past preparatory work.^{7,11} While Aim 2 focuses on examining distributions of change in outcomes and intervention targets rather than testing statistical significance, a priori power calculations using G-Power¹⁰¹ based on intervention effects seen in our prior work⁷ suggest, after accounting for attrition, we will have ~80% power to detect medium effect sizes (d=0.5; $\alpha=0.05$, two-tailed) with an intervention sample of n=19.

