Aim 1. Focus groups will be transcribed verbatim. Qualitative Description¹⁰²⁻¹⁰⁴ using thematic analysis¹⁰⁵⁻¹⁰⁸ as the methodological approach will be used to identify, analyze and report themes and trends across data. A preliminary code book derived from the focus group interview guides will be developed prior to analysis. Codes will be applied to transcripts using NVivo¹⁰⁹ by two individuals to ensure similar understanding of codes and consistency in judgment.¹⁰⁷ Discrepancies in interpretation of the data or application of codes will be resolved. Codebooks will be updated to add data-driven codes; emerging codes will be applied to previously coded text.¹⁰⁸ Codes will then be sorted into themes/subthemes using an iterative process.¹⁰⁸ A descriptive summary will be produced and used to inform the intervention.¹⁰⁴ Intervention user testers (N=3) will provide oral and written feedback related to intervention content, content presentation, and study procedures to better understand the experience of intervention users; materials and procedures will be refined from this feedback.

Aim 2. Descriptive statistics (e.g., mean, percent) will be used to examine feasibility and acceptability data. Change in outcomes (i.e., symptoms, symptom interference) and intervention targets (e.g., self-efficacy, experiential avoidance) from baseline to post-treatment and post-treatment to 4-week follow-up will be examined using paired t-tests. Effect sizes will be computed for the intervention and control arms using Hedges' g_{av} ,¹¹⁰ associated confidence intervals will be examined. Other analyses. Feasibility, acceptability, and patterns of change in outcomes and intervention targets will be examined by sex using descriptive statistics to examine differences that may be obscured when the data is pooled.¹¹¹ We will also examine session completion rates and account for this as necessary in analyses. Our prior work testing videoconferencing symptom management interventions suggests participants will complete 3.4-3.7 of 4 sessions, with 83-90% completing all sessions.^{6,8,9}

Data & Safety Monitoring

- Summarize safety concerns, and describe the methods to monitor research subjects and their data to ensure their safety, including who will monitor the data, and the frequency of such monitoring. If a data monitoring committee will be used, describe its operation, including stopping rules and frequency of review, and if it is independent of the sponsor (per 45 CFR 46.111(a) (6)).

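### The stated 80% power for d=0.5 with 19 intervention participants does not follow from the planned paired t-test: it is about 54% if d is the standardised paired difference, and reaches 80% only with an unstated pre-post correlation of about 0.73

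*Combined protocol and SAP*

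**What the plan says.** The power statement is in section E, Statistical Considerations, under Data Analysis & Statistical Considerations. It reports a G-Power calculation giving, after attrition, about "80% power to detect medium effect sizes (d=0.5", alpha 0.05, "two-tailed) with an intervention sample of n=19". The effect size is said to be "based on intervention effects seen in our prior work". The 19 comes from the intervention arm of 24: "The sample size accounts for 20% attrition, which was derived from our prior work" and from published rates in similar patients. The sentence does not name the test, does not define d and gives no pre-post correlation.

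The Aim 2 paragraph of the same section gives the analysis. Changes from baseline to post-treatment, and from post-treatment to the 4-week follow-up, "will be examined using paired t-tests". "Effect sizes will be computed for the intervention and control arms", using Hedges' g_av with confidence intervals. No other test of change is planned.

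Section E also says that the sample size rests on the pragmatics of recruitment, that the study is not designed for conclusions about efficacy, and that Aim 2 is about distributions of change more than significance.

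**The concern.** A paired t-test on 19 people is a small test, and 80% power for a medium effect looks too high for it. A sample of one arm only, two-sided alpha and a planned paired t-test all point to a within-arm comparison. For such a test the usual input is d_z, and on that input the claimed power is well out of reach.

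At stake is how the within-arm results will be read. Hypothesis H3 expects improvement in the intervention arm that is absent in the control arm. A reader who trusts 80% would take a non-significant intervention result as fair evidence against a d = 0.5 change. On the d_z reading, a true change of that size would be missed about 46% of the time, not 20%. The pilot is also meant to inform a larger trial, and an effect size with no stated scale is a poor basis for that.

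**Working it through.** **Inputs.** From section E: d = 0.5, alpha 0.05 two-sided, 24 randomised to the intervention and 16 to control, 20% attrition. From the Aim 2 paragraph: paired t-test within arm. The sample size reproduces: 24 × 0.8 = 19.2, taken as 19.

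**Power of the paired t-test, d read as d_z.** With n pairs, df = n − 1 and the noncentrality is d_z × √n. Power is the probability that a noncentral t variable falls beyond ± the critical value.

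- n = 19: df = 18, critical t = 2.101, noncentrality = 0.5 × √19 = 2.179.
- Power = 0.541. A simulation of 400,000 trials gave 0.542.
- Shortfall: 0.80 − 0.54 = 0.26.

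**Can another simple reading recover 80%?**

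| Variant at d = 0.5 | Power |
|---|---|
| Paired, n = 19, one-sided | 67.4% |
| Paired, n = 24 (no attrition), two-sided | 65.0% |
| Paired, n = 24, one-sided | 76.8% |
| Paired, n = 21 (10% attrition) | 58.7% |
| Paired, n = 20 (15% attrition) | 56.5% |
| Paired, n = 18 (21% attrition) | 51.6% |
| Two-sample, 19 vs 13 | 27.0% |
| Two-sample, 24 vs 16 | 32.7% |

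The attrition rates of 10%, 15% and 21% are the ends of the two ranges quoted in section E, with the remaining n rounded down. Pooling completers from both arms (19 + 13 = 32) gives 78.2%, but the sentence ties the figure to the intervention sample of 19.

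**What 80% would take on the d_z scale.** At n = 19, d_z must be 0.680. At d_z = 0.5, 34 pairs are needed (80.8%; 33 pairs give 79.5%).

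**Power if d is on the average-SD scale (d_av).** With equal standard deviations at the two times and pre-post correlation r, the standard deviation of the difference is SD × √(2(1 − r)), so d_z = d_av / √(2(1 − r)). For d_av = 0.5 and n = 19:

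| r | d_z | Power |
|---|---|---|
| 0.3 | 0.423 | 41.4% |
| 0.5 | 0.500 | 54.1% |
| 0.6 | 0.559 | 63.5% |
| 0.7 | 0.645 | 75.8% |
| 0.73 | 0.680 | 80.1% |
| 0.8 | 0.791 | 90.3% |

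Solving for 80%: r = 1 − (0.5/0.680)²/2 = 0.729. Correlations from 0.715 to 0.743 give 78% to 82%. A simulation of 200,000 trials at r = 0.73 gave 0.802. The correlations are assumptions, as the documents give none.

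**The case against.** The strongest reply is that the figure is under-specified rather than wrong. The plan never says that d is d_z, and the one effect-size metric it names, Hedges' g_av, uses the average standard deviation. On that scale about 80% is attainable, and the prior work cited as the source of the effect may contain a suitable correlation. This stands in part. The 80% cannot be called impossible, and the 54% depends on the d_z reading. But the reply supplies an input that the plan omits, and the answer depends heavily on it: between r = 0.3 and r = 0.8 the power runs from 41% to 90%.

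A second reply is that 0.73 depends on the model. The power sentence names no test, and the 0.73 assumes equal standard deviations. A one-group repeated-measures F-test over the three assessments, with f = 0.25, gives 72.8% at r = 0.6 and 85.0% at r = 0.7. That is true, but the plan does not include that test, and it too needs a high correlation that is not stated (62.5% at r = 0.5).

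A third reply is that power hardly matters in this pilot. The explicit success criteria are for feasibility and acceptability, no decision depends on this power, and confidence intervals are planned. This stands, and it limits the consequence. It does not make the stated number follow from its inputs.

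**Conclusion.** The concern holds. With the test and inputs that the plan states, about 80% power cannot be reproduced. On the d_z reading it is 54%, about 26 points lower, and the effect detectable with 80% power is d_z = 0.68. On the average-SD reading, 80% requires a pre-post correlation of about 0.73, assuming equal standard deviations at the two times. Both results take the planned two-sided paired t-test at 0.05 with 19 completers. The figure may be recoverable from the cited prior work, but not from the plan as written. The point should be corrected. It does not threaten the design, since N=40 is justified on other grounds.

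**What to change.** Replace the power sentence in section E in one of two ways.

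1. State that, with 19 completers, a two-sided 0.05 paired t-test has 80% power for d_z = 0.68 and about 54% for d_z = 0.5.
2. Define d as the mean change divided by the average standard deviation of the two time points. Give the assumed pre-post correlation (about 0.73 is needed for 80%) and its source. Add the range of power: 41% at r = 0.3, 54% at 0.5, 76% at 0.7 and 90% at 0.8.

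Either version should name the paired t-test. Optionally, add that the same within-arm test in the control arm (16 × 0.8 = 12.8, about 13 completers) has about 38% power at d_z = 0.5. The plan makes no power claim for that arm, but H3 sets the two arms side by side.

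The cost is one sentence. N=40, study conduct and the analysis stay as they are.

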Aim 2: Pilot Randomized Controlled Trial. AYAs with advanced or recurrent cancer (N=40) will be randomized to the intervention or an education control arm using an allocation ratio of 1.5:1. Feasibility of study recruitment (N=40 in 12 months) and participant retention (>80% intervention completion) will be examined along with intervention acceptability. Patterns of change in symptom (i.e., pain, fatigue, distress) severity and interference, self-efficacy for symptom management, and targets of ACT and MCP (e.g., acceptance, experiential avoidance, congruency between values and actions) will be examined. **H2:** Study recruitment and retention will be feasible, and the intervention will be acceptable. **H3:** The intervention arm will evidence improvements in symptom severity and interference, self-efficacy, and targets of ACT and MCP not seen in the control arm.

Background & Significance

- Should support the scientific aims of the research

A. Significance. 1. **Scope of the Problem.** In the last four decades, the incidence of cancer among adolescents and young adults (AYAs; aged 15-29) has increased, and for some cancers (e.g., colorectal cancer, melanoma), has increased more rapidly than for any other age group.⁴³⁻⁴⁵ Improvements in morbidity and mortality outcomes for AYAs have lagged behind both younger pediatric and older adult cancer patients; in fact, AYAs more often present with advanced disease, have more aggressive tumors, and have worse prognosis.¹⁵⁻²¹ Cancer is currently the leading cause of disease-related death among AYAs.⁴⁶ The significant disparity in outcomes for AYAs may stem from a number of age-specific factors that result in decreased access to care and can contribute to delays in diagnosis.⁴⁷ For example, AYAs are more likely to be uninsured or underinsured when compared to younger or older cancer patients.⁴⁸⁻⁵¹ AYAs'

perceptions of invincibility may interfere with attending medical appointments even in the presence of symptoms,⁵² and the relatively low frequency of cancer in this age group may lead medical professionals to attribute an AYA's symptoms to a condition other than cancer.⁴⁹

2. AYAs with advanced cancer have high symptom (e.g., pain, fatigue, emotional distress) burden.^{22,23,53,5}

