Caregivers will also complete at one-time assessment in REDCap. Caregivers will complete a sociodemographic survey (e.g., age, sex, race/ethnicity, education) and a survey about their loved one's cancer treatments. They will also respond to questions asking about their perception of their loved one's self-efficacy for managing symptoms (i.e., modified Self-efficacy for managing chronic disease scale) as well as their own self-efficacy for helping their loved one manage symptoms (i.e., modified self-efficacy for managing chronic disease scale).

The developed intervention will then be reviewed to N=3-5 AYAs with advanced or recurrent cancer to assist with refining intervention content and study procedures. As with focus group/interview participants, user testers will also complete a one-time assessment. Information obtained from user testers will be used to refine the intervention.

D. Aim 2: Pilot RCT. AYAs with advanced or recurrent cancer (aged 15-29) will complete the baseline assessment electronically via Research Electronic Data Capture (REDCap) prior to randomization. The clinical research coordinator will be present at the baseline assessment to assist participants with using REDCap. Participants will then be randomized by the coordinator to the intervention or education control arm using an allocation ratio of 1.5:1. Randomization will be stratified by age (15-19 vs. 20-29). Age categories were chosen to match contemporary definitions of the developmental periods of older adolescence (15-19) and young adulthood (20-29) and echo the definitions of adolescents and young adults adopted by the National Cancer Institute Surveillance, Epidemiology, and End Results Programs.^{13,14} Follow-up assessments will be completed remotely using REDCap on the participant's own or a study-specific device (iPad). Self-report measures have been formatted for use in REDCap. The coordinator will be available via phone in the event of questions or issues.

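### H3 predicts improvement not seen in the control arm, but the Aim 2 analysis prespecifies no between-arm estimate

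*Combined protocol and SAP*

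**What the plan says.** H3 appears under the primary objectives and again under Purpose of the Study, Aim 2: "The intervention arm will evidence improvements in symptom severity and interference, self-efficacy, and targets of ACT and MCP not seen in the control arm".

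The analysis is under Data Analysis & Statistical Considerations, Aim 2. Change "from baseline to post-treatment and post-treatment to 4-week follow-up will be examined using paired t-tests". The text does not say that these tests are run by arm, though that is the natural reading. It continues: "Effect sizes will be computed for the intervention and control arms", using Hedges' g_av, and "associated confidence intervals will be examined". The remaining items are descriptive summaries by sex and an allowance for session completion.

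Section E, Statistical Considerations, sets limits on all this. The study "is not designed to make conclusions about efficacy without further study", and the power sentence opens with the caveat "While Aim 2 focuses on examining distributions of change in outcomes and intervention targets rather than testing statistical significance". The same section gives the intended use: "Information gathered will inform the design of future trials".

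**The concern.** H3 is a statement about a difference between two randomised groups. Every planned analysis of change is either within person or descriptive. No section names a difference in change, a group-by-time term, an ANCOVA, a mixed model, or an interval for a between-arm contrast.

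Setting the two arms' results next to each other is useful description. It does not compare them: one interval excluding zero while the other includes it does not show that the arms differ. The arms are also unequal in size (24 and 16), so the same true change is more likely to reach significance in the intervention arm.

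Two uses are at stake. The results are meant to inform later trials. Background & Significance, B. Innovation, item 3, also makes promising signals one of the conditions for rapid dissemination within the local programme. For both, the useful quantity is the change in the intervention arm beyond the change both arms share.

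**Working it through.** **Inputs.** Randomised numbers are 24 and 16 (A. Study Design). Section E gives 20% attrition, 19 intervention completers and two-sided alpha 0.05. Control completers are not stated. I assume the same attrition: 16 × 0.8 = 12.8, taken as 13. The standardised within-person change d_z (mean change / SD of change) is not given, so I show a range.

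**The plan's own figure.** Section E states about 80% power for d = 0.5 with 19 in the intervention arm. A paired t-test at d_z = 0.5 has noncentrality 0.5 × √19 = 2.18 on 18 df, and power 54%. Power of 80% needs d_z = 0.68. From d_z = d/√(2(1 − r)), that equals d = 0.5 on the raw-score SD only if the pre-post correlation r is about 0.73, which is not stated. The figure concerns the intervention arm alone, and nothing below depends on it.

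**How often could equal change look like H3?** The documents state no decision rule. I assume one for illustration: significant improvement in the intervention arm and not in control. Let p_n be the probability that a noncentral t (n − 1 df, noncentrality d_z√n) exceeds the upper 2.5% point of t on n − 1 df. With the same true d_z in both arms, the chance of the pattern is p_19 × (1 − p_13).

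| d_z in both arms | p_19 | p_13 | Intervention-only pattern |
|---|---|---|---|
| −0.2 | 0.003 | 0.004 | 0.3% |
| 0 | 0.025 | 0.025 | 2% |
| 0.1 | 0.061 | 0.052 | 6% |
| 0.2 | 0.128 | 0.098 | 12% |
| 0.3 | 0.235 | 0.168 | 20% |
| 0.5 | 0.541 | 0.382 | 33% |
| 0.6 | 0.696 | 0.512 | 34% |
| 0.8 | 0.909 | 0.754 | 22% |
| 1.0 | 0.984 | 0.911 | 9% |

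At d_z = 0.5, 16 per arm would give 0.465 × 0.535 = 25%, so the unequal arms add about 8 points. With no attrition (24 and 16) it is 0.650 × 0.535 = 35%. These are chances for a single outcome, not for H3 as a whole.

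**Would a between-arm interval help?** I simulated 19 and 13 completers with equal true change. Among replicates showing the pattern, a two-sample 95% CI for the difference in change excluded zero in favour of the intervention in about 7% at d_z = 0.5 and 11% at 0.3. The interval would usually prevent the misreading.

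**How precise would it be?** The unadjusted half-width is t(30) × √(1/19 + 1/13) = 2.042 × 0.360 = 0.735 SD of change. With ANCOVA and an assumed baseline-to-follow-up correlation of 0.5, it is 2.048 × 0.360 × √(1 − 0.25) = 0.64 SD. (At that correlation the SD of change equals the SD of the score.) Two-sample power for a true difference of 0.5 SD of change is 27%.

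**The case against.** The strongest reply is that this is a pilot. It disclaims efficacy conclusions, plays down significance testing, and aims to describe patterns of change in each arm, which per-arm estimates with intervals do. On that view only one phrase in H3 is out of line. The chance figures rest on a rule the plan does not contain, and 33% to 34% is their peak. The reverse pattern (control significant, intervention not) is also common under equal change: 0.382 × (1 − 0.541) = 17.5% at d_z = 0.5. Much of the effect is therefore small samples rather than a tilt towards the intervention. The planned per-arm intervals would also warn a careful reader: in the simulation, when the intervention-only pattern arose, the two arms' 95% CIs for mean change failed to overlap in only about 1% of cases. Finally, the arms are independent, so a reader could derive a rough difference from the reported results.

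Most of this stands as qualification. The percentages describe a possible misuse, not a stated procedure, and the per-arm intervals deserve credit. The mismatch remains. The disclaimers justify not powering or testing a between-arm effect, but they neither withdraw H3 nor say how it will be judged. The plan still specifies t-tests, so there will be p-values to compare across arms. Overlap of intervals is not a comparison, and a difference each reader must derive is not a prespecified estimate.

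**Conclusion.** The concern holds. The plan prespecifies no estimate of the quantity H3 is about, and this follows from the text without any calculation. The feasibility and acceptability aims are unaffected. It should be fixed before analysis, but it does not undermine the pilot.

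The size of the risk is conditional. Under the assumed rule, equal true change and 19 and 13 completers, the chance per outcome that the results look like support for H3 is negligible if both arms worsen, 2% with no change, and up to about 34% with moderate shared improvement. The documents do not say where in that range this trial would fall.

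**What to change.** 1. For each outcome, add an exploratory between-arm difference at A2 and at A3 from ANCOVA or a mixed model, adjusted for baseline score and the age stratum used in randomisation (15-19, 20-29). Report it with a 95% CI and make no efficacy claim.
2. State that the paired t-tests are run by arm, and label them and g_av as within-arm description.
3. Reword H3, for example: *The between-arm difference in change will be estimated with a 95% CI.*

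If the investigators do not want a between-arm estimate, the minimum is to reword H3 as a description of change within each arm.

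The cost is SAP wording and a modest extra analysis. Arm, age stratum and baseline scores are already collected, and no larger sample is needed. With about nine repeated instruments (the eight in the assessment table plus the FACIT-Sp named in the text) at two follow-ups, there will be at least 18 contrasts. The SAP should say that all are reported as exploratory and how missing follow-up scores are handled. The intervals will be wide (half-width about 0.64 to 0.74 SD under the assumptions above), so the result supports estimation only.

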- Describe the study, providing details regarding the study intervention (drug, device, physical procedures, manipulation of the subject or the subject's environment, etc.). Discuss justifications for placebo control, discontinuation or delay of standard therapies, and washout periods if applicable. Identify procedures, tests and interventions performed exclusively for research purposes or more frequently than standard of care. Include alternative therapies, concurrent therapies discontinued per protocol, risk benefit ratio, and use of tissue/specimens. Discuss monitoring during washout periods if applicable. Include brief description of follow-up, if any.

A. Study Design. We propose to develop a psychosocial symptom management intervention for AYAs with advanced or recurrent cancer and to examine feasibility, acceptability, and patterns of change in outcomes through a pilot RCT. Intervention development will be guided in part by qualitative data from focus groups with: 1) AYAs with advanced or recurrent cancer (n=6/group, 2 groups), 2) caregivers of AYAs with advanced or recurrent cancer (n=8, one group), and 3) a combined caregiver (n=4) and AYA (n=4) group. The intervention and study procedures will be further refined following review by a second group of patient user testers (N=3-5). User testers will review the patient intervention manual and provide feedback to better understand the experience of users and refine the intervention materials and study procedures. It is anticipated that the developed intervention will include traditional behavioral symptom management approaches commonly used in palliative care settings and techniques from MCP and ACT.

The intervention will then be pilot tested through a small RCT. A new group of AYAs with advanced or recurrent cancer (N=40) will be randomized with an allocation ratio of 1.5:1 to the intervention (n=24) or education control (n=16) arms. Participants will complete assessments at baseline (A1), post-treatment (A2; 6-8 weeks after A1), and 4-weeks post-treatment (A3). We will examine feasibility and acceptability, patterns of change in outcomes (i.e., symptoms, symptom interference) and intervention targets (e.g., self-efficacy, acceptance, experiential avoidance) for the intervention and control arms, and sustainability of effects over time.

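### Paired t-tests on change drop anyone missing an assessment; a mixed model on all recorded scores is a cheap improvement, though its gain is modest and the direction of any bias is unknown

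*Combined protocol and SAP*

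**What the plan says.** The Aim 2 paragraph of Data Analysis & Statistical Considerations (E. Statistical Considerations) covers two contrasts: change "from baseline to post-treatment and post-treatment to 4-week follow-up will be examined using paired t-tests". It adds "Effect sizes will be computed for the intervention and control arms using Hedges"' g_av, with confidence intervals, and descriptive summaries by sex. The assessments are baseline (A1), post-treatment at 6-8 weeks (A2) and 4 weeks after treatment (A3).

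Loss appears in the sample-size text: "The sample size accounts for 20% attrition". The figure is supported by 10-15% in the team's own earlier work and 12-21% in mobile-health studies of this age group.

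The nearest thing to a missing-data statement is "We will also examine session completion rates and account for this as necessary in analyses". It concerns intervention sessions, not missing questionnaires, and the control arm has no sessions. The plan states no analysis set, no rule for a missing A2 or A3, no comparison of completers with non-completers and no sensitivity analysis, although the form's prompt asks which subjects will be analysed.

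The Risk/Benefit Assessment and Data & Safety Monitoring sections both say that participants with increased or extreme distress will not be kept in the trial. Distress is also an outcome, measured by the PROMIS depression and anxiety scales.

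**The concern.** A paired t-test drops anyone who lacks either score. No other set of participants is named for g_av, so it rests on the same pairs. Three things follow.

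- Baselines already recorded for those lost before A2 play no part in the estimated change.
- A1-A2 and A2-A3 may rest on different people, which weakens the planned look at whether effects last.
- If loss is related to symptoms, the completers' change is not the change in the randomised arm. The distress rule makes some symptom-related loss foreseeable, though the plan gives no size for it.

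The pilot disclaims efficacy conclusions, so no confirmatory claim is at risk. What is at stake is the within-arm effect sizes and intervals, which are a planned product and are meant to inform the design of later trials.

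**Working it through.** **The plan's own figure.** 24 × 0.8 = 19.2, which matches the stated 19 in the intervention arm. For the control arm, 16 × 0.8 = 12.8, about 13. Roughly 8 of 40 would be absent from a change analysis if all the loss falls on assessments.

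**Assumptions not in the documents.** Scores are in SD units, a higher score is worse and a negative change is improvement. The A1-A2 correlation is r = 0.4 to 0.7. Loss follows a logistic model with odds multiplied by 1.65, 2.7 or 4.5 per SD. All 20% is lost before A2.

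**Loss driven by the baseline score.** Let m be the amount by which the completers' mean baseline lies below that of all randomised. Then

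bias of completers' change = (1 − r) × m.

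Integrating the logistic model over a standard normal baseline at 20% loss gives m = 0.096, 0.172 and 0.227 for the three odds ratios.

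- Smallest: (1 − 0.7) × 0.096 = 0.03 SD.
- Central: (1 − 0.6) × 0.172 = 0.07 SD.
- Largest: (1 − 0.4) × 0.227 = 0.14 SD.

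Against the planning effect of 0.5 that is 6% to 27%. The sign is positive, so completers appear to improve less. At 10% loss, m = 0.090 for the central odds ratio and the bias is 0.4 × 0.090 = 0.04 SD.

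**Likelihood estimate from the same data.** With two time points this is the completers' A2 mean, plus the regression slope of A2 on A1 times (mean A1 of all randomised − mean A1 of completers), minus the mean A1 of all randomised. Simulated with n = 24, r = 0.6, 20% lost, odds ratio 2.7 and true change zero:

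| Loss driven by | Paired bias (RMSE) | Likelihood bias (RMSE) |
|---|---|---|
| Baseline score | +0.07 (0.214) | 0.00 (0.206) |
| Worsening, A1 to A2 | −0.155 | −0.127 |
| Post-treatment score | −0.07 (0.215) | −0.12 (0.232) |
| Overall level, A1 and A2 | 0.00 | −0.07 |

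The RMSE gain in the first row is (0.214 − 0.206)/0.214, about 4%.

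**Completely random loss.** Variances are 2(1 − r)/19 for the paired estimate and (1 − r²)/19 + (1 − r)²/24 for the likelihood estimate. The saving is 3% (r = 0.7) to 6% (r = 0.4). This ignores estimation of the slope; simulated, the saving is about 1% to 5%.

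**What the unseen scores could do.** If completers improve by 0.5 SD and 20% are missing, the mean change of all randomised is:

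- 0.8 × (−0.5) + 0.2 × 0 = −0.40 if those lost did not change;
- 0.8 × (−0.5) + 0.2 × 0.5 = −0.30 if they worsened by 0.5 SD;
- 0.8 × (−0.5) + 0.2 × 1 = −0.20 if they worsened by 1 SD.

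At 10% loss the same three values are −0.45, −0.40 and −0.35.

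**The case against.** The strongest reply is that the mixed model is not a demonstrated correction. It removes the bias when loss depends on recorded scores. Removal for distress that arises during the study looks more like loss driven by worsening or by the later score. In the first of those cases the model helps only a little; in the second it is more biased than the paired test. This stands, and it is why the paired result should be kept and a shift analysis added.

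Size is also a fair objection. A bias of 0.07 SD is about a third of the standard error, √(2 × 0.4/19) = 0.205. The upper end of the range needs both a steep odds ratio and a low correlation. The plan does not say when the 20% is lost, and its Study Measures section describes attrition by session completion; someone who misses a session can still complete A2 remotely. Later or smaller loss shrinks the A1-A2 bias. If dropout is strictly monotone, the A2-A3 set is nested in the A1-A2 set, though it is still a different set once anyone is lost between them.

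Finally, this is a pilot, and feasibility and acceptability are summarised descriptively and are unaffected. That limits the weight of the point but does not remove it, because the effect sizes are meant to be carried forward.

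**Conclusion.** The point holds as a cheap improvement. The stated analysis of change uses complete pairs, the expected loss is allowed for only in the sample size, and nothing says how missing A2 or A3 scores are handled. Under loss that depends on recorded baseline symptoms, the completers' change is biased by about 0.03 to 0.14 SD at 20% loss, with a central value of 0.07, or about 0.04 at 10% loss. These figures rest on the assumed odds ratios and correlations and on all loss falling before A2.

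Two stronger readings are tempting. A reader might infer that the results will describe those who stayed well enough to answer, and so flatter the intervention. The documents give no reasons for attrition, and losing patients who are sicker at baseline biases towards less apparent improvement, so no direction can be asserted. A reader might also infer that a mixed model cures the problem. It does so only under missing-at-random; the other mechanisms in the table leave bias, in two of them more than the paired test does.

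**What to change.** In the Aim 2 analysis paragraph:

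1. As the main analysis of change, fit one linear mixed model per outcome to all available A1, A2 and A3 scores of all randomised participants. Use time by arm, an unstructured covariance with a named simpler fallback if it does not converge, and Kenward-Roger degrees of freedom. Read the A1-A2 and A2-A3 changes in each arm, with confidence intervals, from this model.
2. State how the standardised effect is formed, for example model-based change divided by the average of the A1 and A2 SDs (and likewise A2 and A3 for the second contrast).
3. Keep the paired t-test and g_av, labelled as a completer analysis, and report both.
4. Tabulate by arm the numbers and baseline scores of those with and without A2 and A3, and report deaths by arm.
5. Add a simple shift (delta) analysis that moves the missing scores by stated amounts, since neither main nor completer analysis tests departures from missing-at-random.
6. Say that the effect sizes are pilot estimates only.

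The cost is analysis wording and a few lines of code, with no new data or participants. The downsides are possible non-convergence at N = 40, reliance on missing-at-random and a small gain in precision.
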